10.0 Sharing of Results with Subjects

10.1 *Describe whether you will share results (study results or individual subject results, such as results of investigational diagnostic tests, genetic tests, or incidental findings) with subjects or others (e.g., the subject's primary care physician). If so, describe how you will share the results and include this information as part of the consent document. Upload materials you will use to explain the results to subjects:*

We will not share any results with the study participants. In the event of incidental findings, we will follow the established protocol highlighted in the NIAAA Data and Safety Monitoring Plan (DSMP) for the R01 associated with this project. As an example, we will review our current procedure for handling incidental neuroimaging findings below:

Specific to incidental neuroimaging findings: The Human Neuroimaging Lab at Virginia Tech has a standardized approach to incidental findings across approximately 60 currently active protocols (including scanning over 150 individuals with AUD). Moreover, our process is consistent with the best practices recommendations of the NIMH "MRI Research Safety and Ethics: Points to Consider" whitepaper (https://www.nimh.nih.gov/about/advisory-boards-and-groups/namhc/reports/mri-research-safety-ethics_33826.pdf). Furthermore, our procedures conform with those reported in the literature as appropriate for our research setting. During the consenting process, participants are informed that the scans that will be performed in the study are not the same as those that would be used in a clinical setting, and thus have limited diagnostic value. Further, some of the scans require subsequent data analysis and would never be read by a neuroradiologist. As is common and acceptable in many academic institutions, we do not have a neuroradiologist on staff to read every scan. Our policy (which is communicated to all participants verbally and written in the consent document):

"This is not a study to diagnose these structures. Your brain images will not be read by a doctor who specializes in reading brain images. If something abnormal is observed by chance, we will tell you. You will then be counseled as to what clinical referral would be appropriate. We are not qualified to make any diagnosis, nor is this fMRI of diagnostic quality for medical purposes. In the event of an incidental positive pregnancy test finding, the study personnel will share the results with you. They will counsel you as to what clinical referral might be appropriate."

We also communicate, however, that we will err on the side of caution in communicating with them if we do observe a possible abnormality. The DSMB will review these procedures, and their adequacy of protection against risk, at each semi-annual DSMB meeting.

11.0 Study Timelines

11.1 Describe:

- *The duration of an individual subject's participation in the study (for example, 1 hour, 2-4 weeks, 3-5 years).*
- *The amount of time expected to enroll all study subjects (weeks, months, years, etc.)*
- *The amount of time expected for the investigators to complete this study including primary data analyses.*

The total study is expected to take up to approximately 15 weeks. The study team has projected this study to take approximately 2 years to complete enrollment and data analysis.

Time	Session 1	Session 2	Baseline Monitoring	Session 3 - fMRI then Group Assignment		Monitoring Part 1	Session 4	Monitoring Part 2	Session 5 (fMRI)	Session 6 - 1 month follow up
All Participants	✓	✓	~ 7 days	fMRI	→ EFT	~ 14 days	✓	~ 14 days	✓	✓
				fMRI	~ CET		✓		✓	✓

12.0 Inclusion and Exclusion Criteria

12.1 Describe how you will screen individuals for eligibility. When will screening occur and what procedures will you use? Upload any screening scripts or surveys to Protocol Management:

We have developed and are currently using a separate pre-screening survey (online/phone pre-screen), which occurs prior to enrolling participants into our intervention protocols.

This pre-screening ensures that participants are likely to meet all inclusion/exclusion criteria (e.g., MRI scanner eligibility) prior to enrolling into any randomized study. This initial pre-screening (online/phone) may be completed online or over the phone. Information is stored in REDCap, which is HIPAA compliant and password protected. If participants seem eligible from the online/phone screen, they will be scheduled for the in-lab screen in the laboratory to further determine eligibility and appropriateness for this specific intervention-based study.

12.2 Describe the eligibility criteria that define who will be included and who will be excluded from enrollment for each procedure of your study.

Include any geographic criteria (e.g., Virginia Tech undergraduate students, a national sample of adults with engineering degrees, minors aged 8-12 in the New River Valley, university faculty in Virginia and Paris, France):

Inclusion criteria for signing consent will require that participants: (1) demonstrate high-risk or harmful drinking (AUDIT>15; i.e., 16 or higher), (2) be between 21-65 years old, and (3) have a desire to quit or cut down on their drinking, but do not have proximate plans to enroll in treatment for AUD during the study period.

Exclusion criteria include: (1) meeting moderate to severe DSM-5 criteria for substance-use disorders other than alcohol, nicotine, or marijuana, (2) having a current diagnosis of any psychotic disorder, (3) having a history of seizure disorders or traumatic brain injury they have not fully recovered from, (4) having any contraindication for participation in the fMRI session, or (5) reporting current pregnancy or lactation.

12.3 Indicate specifically whether you will include or exclude each of the following special populations: (You may not include members of these populations as subjects in your research unless you indicate them in the description of your subject population.)

- *Minors, as defined by state law where the study is performed (infants, children, teenagers)*
- *Pregnant women (can be included in minimal risk studies by mentioning in section 13.1)*
- *Prisoners (including all incarcerated individuals)*
- *Adults not capable to consent on their own behalf*

This project will focus on individuals with alcohol use disorder, aged 21 to 65. We will not include individuals under the age of 21 in compliance with Virginia state law.

Vulnerable subjects, such as individuals with cognitive impairments, minors, prisoners, and pregnant women will be excluded.

13.0 Vulnerable Populations

13.1 If the research involves individuals who are vulnerable to coercion or undue influence, please describe additional safeguards you will include to protect their rights and welfare. Consider the applicable items listed below:

- *If the research involves Virginia Tech students, indicate whether these are students of any of the investigators. If so, describe whether the activities will take place during class time as part of the curriculum and the steps you will take to reduce the possibility that students feel obliged to participate in order to improve their course grade. The HRPP can provide further guidance as needed. Describe whether you will request access to student records (e.g., SAT, GPA, GRE scores).*
- *If the research involves employees of Virginia Tech or the research sponsor, describe steps you will take to ensure that the employees are freely participating and describe how their data will be protected from inspection by their supervisors.*
- *If the research involves Virginia Tech NCAA athletes, you must obtain approval from the athletic department.*
- *For research involving Montgomery County Public Schools, you must obtain county approval (after obtaining contingent Virginia Tech approval). Other locales have different requirements; please check on these and describe here. Approval is typically granted by the superintendent, principal, and classroom teacher (in that order). Approval by an individual teacher is insufficient. School approval, in the form of a letter or a memorandum should be uploaded as a supporting document.*
- *If the research involves pregnant women, review “CHECKLIST: Pregnant Women (HRP-412)” to ensure that you have provided sufficient information in this protocol.*
- *If the research involves prisoners, review “CHECKLIST: Prisoners (HRP-415)” to ensure that you have provided sufficient information in this protocol.*
- *If the research involves persons who have not attained the legal age for consent to treatments or procedures involved in the research (minors), review the “CHECKLIST: Minors (HRP-416)” to ensure that you have provided sufficient information in this protocol.*
- *If the research involves cognitively impaired adults, review “CHECKLIST: Cognitively Impaired Adults (HRP-417)” to ensure that you have provided sufficient information in this protocol.*

This research study will not include any vulnerable populations.

14.0 Number of Subjects

14.1 Indicate the total number of subjects to be enrolled and how this number was determined (e.g., sample size calculation [show], number of available subjects in a finite pool, number of tests funding award would allow):

Although we have observed large effect sizes of EFT on DD in AUD participants in our preliminary studies (pre-post $d=1.6$; post-only $d = 0.68$), we used a more conservative medium effect size ($f= 0.25$) to inform sample sizes to increase power to detect effect on the broader range of measures proposed here (e.g., intensity of demand). Using the method proposed by Borm, Fransen, and Lemmens, and a pre- and post-measurement correlation of 0.70218, 76 total participants would be needed to complete this study (38 participants per group), assuming a type 1 error rate of 0.01 and 95% statistical power, based on an ANCOVA comparing the intervention while using the baseline measure as a fixed-effect covariate in the analysis.

We have been successfully recruiting individuals with AUD in our community for the past 8 years. Based on these 8 years of experience recruiting alcohol users into studies of comparable length and complexity, we anticipate that over 80% of consented participants will be eligible (i.e., randomized) and about 65% of those eligible individuals will complete this study. Thus, to achieve a final sample size of 76, we anticipate consenting 200 participants. We plan to enroll more than our average attrition rate because of the increased procedures and the time demands of the study.

14.2 If this is a multi-site study, indicate the number of subjects to be enrolled at this site and the total to be enrolled from all sites:

N/A

14.3 If applicable, indicate the number of potential subjects you expect to screen for enrollment, and the number of subjects you will need to complete the research procedures:

We have developed and are currently using a separate pre-screening protocol, which occurs prior to enrolling participants into our intervention protocols, in order to effectively decrease attrition in our studies by ensuring that participants meet most inclusion/exclusion criteria (e.g., MRI scanner eligibility) prior to enrolling into the randomized study. Given that this separate screening protocol is used for all currently ongoing studies in the lab, we cannot accurately estimate the total number of potential participants we expect to screen. However, as described above, we anticipate enrolling 200 participants in order to complete a total of 76 participants. We plan to enroll more than our average attrition rate because of the increased screening procedures and the time demands of the study. Additionally the first few participants enrolled into the study may be pilots.

14.4 If the study has more than one procedure, indicate the total number of subjects to undergo each procedure separately:

All participants will undergo all sessions unless they withdraw from the study.

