5.0 Study Design and Statistical Analysis Plan

5.1 *Describe the basic study design/approach (e.g., qualitative study using five focus groups of first year students to describe assimilation into the university community; randomized controlled trial of a behavioral change intervention to increase dietary intake of whole grains; pre- post-test evaluation of new pedagogical techniques to improve adult literacy):*

Participants will be randomly assigned to experimental or control groups, stratified by demographic characteristics (e.g., drinks per day and baseline delay discounting rates). Based on our 8 years of experience recruiting this population, we expect approximately 66% retention among eligible participants. Therefore, we will enroll approximately 200 participants in order to conclude with 76 completers. We plan to enroll more than our average attrition rate because of the increased screening procedures and the time demands of the study. Randomization will be stratified on demographic characteristics (e.g., drinks per day and baseline delay discounting rate). As a result, any differences observed in our primary hypotheses will not be confounded by these variables.

EFT group participants will be asked to think about and describe the most positive event that could realistically happen at a number of delays in the future (e.g., 1 day, 2 weeks, 1 month, 1 year, 5 years, 25 years). In contrast, participants randomized to the CET condition, will be asked to think about and describe the most positive event that occurred at a number of time points from the recent past (e.g., last night from 7pm-10pm, yesterday between 4pm-7pm, yesterday between 1pm-4pm, yesterday from 10am-12pm, yesterday between 7am-10am, the night before last between 7pm-10pm, and evening before last between 4pm-7pm).

5.2 *Describe corresponding data analysis plan/approach (e.g., content analysis of focus group transcripts; descriptive analysis followed by linear regression modeling; nonparametric analysis of pre- and post-test measures):*

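### Protocol 14.1: 76 completers give about 66% power under the stated ANCOVA inputs, not 95%; those inputs need about 148 completers

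*Protocol*

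**What the plan says.** Protocol section 14.1 gives every input to its calculation except the sidedness of the test:

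- Effect size: after citing larger pilot effects on delay discounting (pre-post d = 1.6, post-only d = 0.68), it says "we used a more conservative medium effect size ($f= 0.25$) to inform sample sizes".
- Correlation: "a pre- and post-measurement correlation of 0.70218".
- Result and error rates: "76 total participants would be needed to complete this study (38 participants per group), assuming a type 1 error rate of 0.01 and 95" percent power.
- Analysis: "based on an ANCOVA comparing the intervention while using the baseline measure as a fixed-effect covariate in the analysis".

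Section 5.1 repeats the target ("we will enroll approximately 200 participants in order to conclude with 76 completers"), and so does section 14.3.

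The SAP, under Sample size, uses the same f and alpha but another method: a within-between interaction in a repeated-measures ANOVA, correlation 0.5, 80% power and 52 completers.

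**The concern.** An f of 0.25 at alpha 0.01 with 95% power is a demanding specification. A correlation of 0.70 roughly halves the sample that an unadjusted comparison needs, but the unadjusted requirement is close to 300, so 76 looks too small by about a factor of two.

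The 95% figure is the protocol's justification for its size, and 14.1 says the smaller effect was chosen so that the trial would be adequate for outcomes beyond delay discounting, such as demand intensity. If true power for that effect is far lower, a null result on demand, craving or drinking would be read as stronger evidence of no effect than the design can supply.

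**Working it through.** **Inputs (Protocol 14.1).** f = 0.25, so d = 2f = 0.5 for two equal groups; r = 0.70218 as printed (r = 0.70 was also tried, in case the last digits are a fused reference number); alpha = 0.01; power 95%; N = 76, 1:1. Sidedness is not stated; two-sided is assumed and one-sided is checked.

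**1. Attempt to reproduce 76 as described.** For an ANCOVA with one baseline covariate, power follows from a noncentral F with 1 and N − 3 degrees of freedom and noncentrality λ = N f² / (1 − r²).

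- 1 − 0.70218² = 0.507
- At N = 76: λ = 76 × 0.0625 / 0.507 = 9.37, power **66.1%** (65.8% with r = 0.70)
- At N = 148: λ = 148 × 0.0625 / 0.507 = 18.25, power **95.0%** (94.9% with r = 0.70, where 150 is needed)

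The stated figure does not reproduce.

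**2. Cross-checks on the required number.**

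- An unadjusted two-group comparison needs 290 in total (145 per group). Multiplying by 1 − r²: 290 × 0.507 = 147, or 74 per group after rounding up.
- The normal approximation gives 73 per group, 146 in total, with 68.6% power at 38 per group.

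**3. Variants that might rescue 76.**

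| Variant | Power at 76 | N for 95% |
|---|---|---|
| As stated, two-sided 0.01 | 66.1% | 148 |
| r = 0.70 | 65.8% | 150 |
| One-sided 0.01 | 75.1% | 132 |
| Two-sided 0.05 | 85.6% | 108 |
| d = 0.68 (pilot, post-only), two-sided 0.01 | 93.2% | 82 |

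No variant that keeps the stated method, f, r, alpha and power gives 76. To reach 95% with 76 completers, the ANCOVA needs f of about 0.353 (d of about 0.71) or r of about 0.864.

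**4. A calculation that does give 76.** For the interaction in a two-group, two-occasion repeated-measures ANOVA, λ = 2 N f² / (1 − ρ) with 1 and N − 2 degrees of freedom. With ρ = 0.5 and alpha 0.01:

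- N = 76: λ = 2 × 76 × 0.0625 / 0.5 = 19, power 95.4% (94.8% at 74, so 76 is the smallest even N)
- N = 52: power 81.8%, which matches the SAP's 52 for 80%

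With ρ = 0.70218 the same formula needs only 46, so 14.1's own correlation does not lead to 76 by this route either.

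The effect size also changes meaning. If δ is the between-group difference in change, in SD units of a single measurement, the change score has variance 2(1 − ρ) and the squared noncentrality is Nδ² / [8(1 − ρ)]. Setting this equal to 2Nf² / (1 − ρ) gives δ = 4f = 1.0. So f = 0.25 there is a 1.0 SD difference, twice the 0.5 SD it represents in the ANCOVA and larger than the pilot post-only d of 0.68. That 76 came from this calculation is an inference; the mismatch in step 1 does not depend on it.

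**5. Does over-enrolment cover the gap?** At the rates in 14.1 (80% eligible, 65% of those completing), 200 × 0.80 × 0.65 = 104 completers. Power at 104 under the stated inputs is 82.8%.

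**The case against.** The strongest reply is that 66% describes a calculation the trial may never run. Protocol 5.2 plans a mixed-effects model with day, pre/post period and group, and the SAP plans Poisson mixed models of daily drinks, so neither can be given a power from these inputs. The SAP also sets 0.05 for all analyses, with multiplicity corrections it does not specify; at an uncorrected 0.05 the same ANCOVA has about 86% power at 76. For delay discounting itself, the pilot post-only effect gives 93%. The latest protocol entry (10/15/2024) is logged only as a change of PI, so 14.1 may simply be stale text. And since 76 matches the SAP's method at 95% power, 14.1 may misdescribe its method rather than miscalculate its N.

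Much of this stands as context. The 34% risk of missing the effect is conditional on alpha 0.01, 76 completers and the ANCOVA. The possibility that the description, not the number, is at fault means the fix should allow either correction. None of it makes the statement in 14.1 true: that section commits to alpha 0.01, to f = 0.25 and to ANCOVA with a correlation near 0.70, and those four together do not give 95% power at 76. Stale or not, the current protocol still carries the figure.

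**Conclusion.** The concern holds. Under the inputs stated in 14.1, 76 completers give about 66% power rather than 95%, and 95% needs about 148 (150 if the correlation is exactly 0.70). The chance of missing the stated effect is then about 34% instead of 5%.

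This assumes a two-sided test, equal groups and a single baseline-adjusted post score. Neither the one-sided reading nor the exact value of the correlation changes the conclusion. The mismatch sits alongside a second one: the SAP's target of 52 at 80% power reproduces by its own method, but under the protocol's ANCOVA inputs 52 completers would have about 45% power.

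**What to change.** Correct section 14.1 so that method, inputs, N and power agree, and state the sidedness. If the ANCOVA description is what was intended, suitable text is:

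> With 76 completers (38 per group), a baseline-adjusted ANCOVA has about 66% power at two-sided alpha 0.01 to detect d = 0.5 (f = 0.25), assuming a pre/post correlation of 0.70. Power of 95% is reached for d of about 0.71.

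If the 95% claim for f = 0.25 is kept instead, the matching target is about 148 completers. At the protocol's own rates that means about 285 consented (148 / (0.80 × 0.65) = 284.6).

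If the repeated-measures interaction was the real basis, name it, give its correlation of 0.5, and say that f = 0.25 there is a 1.0 SD difference in change. The description of that effect as medium and conservative would then have to go.

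Carry the corrected target to sections 5.1 and 14.3, and reconcile it with the SAP's 52 at 80% so that one target, one alpha and one power figure apply to the trial.

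Restating the power costs protocol and SAP wording only and needs no extra participants. The price is a less favourable power statement.

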15.0 Recruitment Methods

15.1 Describe when, where, and how you will recruit potential subjects:

Participants will be recruited from the community via posted or mailed flyers/postcard, word of mouth, and electronic advertisements (e.g., Craigslist, Facebook). Participants will be contacted if they have given prior permission (through previous informed consent form) or by completion of a confidential pre-screening questionnaire. Services from mailing list companies may be used.

Group posting rules will be checked and followed when posting to community pages. If posting requires approval, or if it is unclear if our post meets group rules, the research staff will send the following message to a group administrator along with the picture/post to be shared: "Hello! My name is _____ and I work for the _____ lab(s) at the Fralin Biomedical Research Institute at Virginia Tech Carilion. We are currently recruiting for an Institutional Review Board approved study which investigates decision-making in individuals who drink alcohol. Would it be alright if I posted the attached ad to this group for those who might be interested in participating?" All posted materials, including captions and images, will be submitted to and approved by the VT IRB prior to reaching out to community pages. In situations where the post would violate group rules or is rejected by a page administrator, it will not be shared on that page. If an administrator reaches out to the study staff following posting and requests the post be taken down, it will be taken down.

In addition, we will partner with BuildClinical to accelerate enrollment. BuildClinical is a data-driven platform that helps academic researchers recruit participants for research studies more efficiently using social media, software, and machine learning. They have worked with IRBs in the US to ensure adherence to all the appropriate guidelines and procedures. They utilize study-specific advertisements to engage participants on digital platforms such as Facebook, Google, WebMD, etc., and redirect them to a study-specific landing page should they click it. On the landing page, the person can complete an online pre-screen questionnaire that gets routed into BuildClinical's platform. BuildClinical's Secure Socket Layer (SSL) software, which encrypts all inputted information is HIPPA compliant and keeps potential participant information private.

15.2 Describe the source of subjects (for example, clinic patients with specific conditions, students in the library, community members at a gathering, or members of a local gym):

Participants will be recruited from the community via posted or mailed flyers/postcards, word of mouth referrals, and electronic advertisements (e.g., Craigslist, Facebook). Participants will be contacted if they have given prior permission (through previous informed consent form) or by completion of a confidential pre-screening questionnaire. Services from mailing list companies may be used.

In addition, we will partner with BuildClinical to accelerate enrollment. BuildClinical is a data-driven platform that helps academic researchers recruit participants for research studies more efficiently using social media, software, and machine learning. They have worked with IRBs in the US to ensure adherence to all the appropriate guidelines and procedures. They utilize study-specific advertisements to engage participants on digital platforms such as Facebook, Google, WebMD, etc., and redirect them to a study-specific landing page should they click it. On the landing page, the person can complete an online pre-screen questionnaire that gets routed into BuildClinical's platform. BuildClinical's Secure Socket Layer (SSL) software, which encrypts all inputted information is HIPPA compliant and keeps potential participant information private.

15.3 Describe the methods that you will use to identify potential subjects:

Participants will be recruited from the community via posted or mailed flyers/postcards, word of mouth referrals, and electronic advertisements (e.g., Craigslist, Facebook). Participants may contact the lab directly via email, facebook, phone, walk-in, face-to-face at tabling events, or completing the online pre-screening questionnaire. Participants will also be contacted directly if they have given prior permission (through previous informed

consent form) or by completion of a confidential pre-screening questionnaire. Services from mailing list companies may be used.

In addition, we will partner with BuildClinical to accelerate enrollment. BuildClinical is a data-driven platform that helps academic researchers recruit participants for research studies more efficiently using social media, software, and machine learning. They have worked with IRBs in the US to ensure adherence to all the appropriate guidelines and procedures. They utilize study-specific advertisements to engage participants on digital platforms such as Facebook, Google, WebMD, etc., and redirect them to a study-specific landing page should they click it. On the landing page, the person can complete an online pre-screen questionnaire that gets routed into BuildClinical's platform. BuildClinical's Secure Socket Layer (SSL) software, which encrypts all inputted information is HIPPA compliant and keeps potential participant information private.

15.4 Describe materials that you will be use to recruit subjects. Attach copies of these documents with this protocol in Protocol Management and be sure to include the IRB protocol number on each document.

- *For flyers, attach the final copy of printed flyers.*
- *For Virginia Tech News, Facebook postings and ads, newspaper ads, websites, MTurk/SONA/online survey systems, etc., attach the final wording and graphics to be used.*
- *For email recruitments, please include the subject line.*
- *For advertisements meant for audio broadcast, please submit the wording of the advertisement prior to taping (to avoid having to re-record with approved language) and submit the final recorded version for IRB review before use.*
- *Describe any compensation to subjects. Separate compensation into appropriate categories, such as: reimbursement for expenses, time and effort, and additional incentives for study participation. For each category, specify the amount (including any pro-rated amount), schedule, and method of payment.*

Flyers to be used in community and online posting are attached.

Compensation. The compensation for this study is based an hourly rate of approximately \$20/hr. Compensation also includes incentives for participant performance and attendance.

Compensation will follow the following schedule:

Session 1 = \$15

Session 2 = \$25

EPISODIC THINKING AND ALCOHOL USE IRB 22-358

Baseline Monitoring = \$1 for daily self-reports and \$1 per BAC sample submission (x3). During baseline monitoring, participants who submit all required reports in a given day will receive a \$1 bonus for that day. Thus they can receive \$1 per information submitted or \$5 for submitting all required information.

= up to \$35 (for 7 days; total amount will be more/less depending on the exact number of baseline monitoring days completed by participant)

Session 3

MRI = \$15**

Session = \$30

Monitoring Part 1 = \$1 for daily self-reports and \$1 per BAC sample submission (x3), and \$1 per reply to cue text (x2). Participants who submit all required reports in a given day will receive a \$4 bonus for that day. Thus they can receive \$1 per information submitted or \$10 for submitting all required information.

= up to \$140 (for 14 days; total amount will be more/less depending on the exact number of monitoring days completed by participant)

Session 4

Session = \$30

Monitoring Part 2 = \$1 for daily self-reports and \$1 per BAC sample submission submission (x3), and \$1 per reply to cue text (x2). Participants who submit all required reports in a given day will receive a \$4 bonus for that day. Thus they can receive \$1 per information submitted or \$10 for submitting all required information.

= up to \$140 (for 14 days; total amount will be more/less depending on the exact number of monitoring days completed by participant)

Session 5

MRI = \$15**

Session = \$30

Session 6 = \$50

Study Completion Bonus***: \$150

***Participants receive if they complete all six sessions

As an incentive for session attendance, participants may participate in a fishbowl drawing contingent upon arriving on time for the sessions. Some fishbowl drawings may result in receipt of either a small, medium, or large prize and some may result in verbal positive reinforcement. The prizes may be in the form of \$1.00, \$5.00, and \$10.00 rewards. The odds of receiving a prize will be: "Good Job" (odds 13/50), \$1 (odds 25/50), \$5 (odds 10/50), \$10 (odds 2/50).

Additionally, participants will be eligible for a \$10 Scan bonus** per MRI. Participants will receive this bonus if they remain still and awake for the fMRI scan.

Total Compensation: approximately \$700 for completion of all sessions and remote reports, plus bonuses.

We note that compensation will be prorated proportional to the amount of sessions or duration of session completed.

In addition, scheduling barriers will be minimized by offering participants a flexible session schedule and travel compensation, if necessary, etc.

Participants may be compensated for travel expenses (i.e., travel time) if traveling from outside of Roanoke to Roanoke for study sessions. For example, traveling from Blacksburg to Roanoke for a study session. In these cases, participants will receive additional compensation consistent with minimum wage (e.g., approximately \$10 per hour) for their round trip travel. Currently there are no costs for parking at the FBRI, where the study sessions occur.

To allow for payments that are both convenient and rapidly available, we may pay participants with reloadable prepaid cards through Greenphire ClinCard (www.greenphire.com), an FDIC-insured payment provider that specializes in clinical trial stipend payments that comply with IRB privacy regulations and considerations. At the beginning of the study, the participant will receive a prepaid MasterCard debit card that can be used anywhere that accepts MasterCard. As payments are earned in the course of the study, additional funds will be added to the account for that participant. Payments will be added to the participant's ClinCard within 24 hours of the session completion. Funds are immediately available when added and participants can check their balance as desired. This system will allow frequent, immediately available payments. Payments may also be made via check or cash; however remote debit card payments and checks will be used most often.

